## **9. OUTCOME MEASURES**

### **9.1 Primary outcome measure**

The primary outcome measures for drug efficacy will be:  
Performance on neuropsychological testing and responses to parent questionnaire.

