**Précis:**

**Objective:** To perform a clinical trial assessing the safety, tolerability and efficacy of the GABA(B) receptor antagonist SGS-742 in patients with SSADH deficiency.

**Study Population:** Twenty-two children and adults with SSADH deficiency.

**Design:** Double-blind, cross-over, phase II clinical trial. SGS-742 is a GABA (B) receptor antagonist that has shown to be safe and well-tolerated in clinical trials in adults with cognitive impairment. In addition, preliminary data in the SSADH knockout mouse model suggest efficacy in this specific syndrome. The primary outcome measure will be a change in the Auditory Comprehension subtest of the Neuropsychological Assessment Battery Language Module score; the secondary outcome measure will be a change in cortical excitation and inhibition measured by transcranial magnetic stimulation (TMS). Additional evaluations will include neurological and neuropsychological examinations, magnetic resonance spectroscopy and CSF collection to measure GABA levels. The trial will have a baseline phase in which each patient will undergo a neurological examination and a neuropsychological evaluation. During the subsequent treatment phase, patients will be randomized to SGS-742, supplied by IRIX Pharmaceuticals, and based on weight given a maximum tolerated dose not to exceed 600 mg t.i.d. orally, or placebo, each for 6 months. Patients will then have repeat TMS, neurological and neuropsychological evaluations, followed by cross-over to the alternate treatment arm, and re-evaluation after 6 months.

**Outcome Measures:** The primary outcome measures for drug efficacy will be performance on neuropsychological testing and responses to parent questionnaire. The secondary outcome measure will be TMS parameters of cortical excitation and inhibition. The outcome measures for safety will include clinical examination and neuropsychological tests.

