### **2.1 Hypotheses:**

H1: Patients will show improvement in the Auditory Comprehension subtest of the Neuropsychological Assessment Battery Language Module during treatment with SGS-742 and improvements in activities of daily living based on parent questionnaire.

H2: Patients with SSADH deficiency will have lengthening toward normal values of the cortical silent period, and return of long interval intracortical inhibition, during a therapeutic trial of SGS-742

H3: Patients will show improvement on global assessment ratings

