#### 4.4.4 Neuropsychological Assessments

Patients will undergo comprehensive language and cognitive evaluations using a selection of assessments based on age and ability such as the following:

1. WNV (Wechsler Nonverbal Scale of Ability) for patients up to age 22, an individually-administered, standardized test that provides an IQ score and insights into cognitive functioning. The test requires approximately 30 minutes to administer.
2. WAIS-IV (Wechsler Adult Intelligence Scale) for patients age 22 and older, also an individually-administered test of ability will be administered using the subtests that overlap the WNV. These are nonverbal because of the language limitations of this population.
3. The Neuropsychological Assessment Battery: Language Module. Subtests to be administered include confrontation Naming and following directions (Auditory Comprehension) to assess language competence.

4. Rule Shift from the Behavioral Assessment of Dysexecutive Syndrome is a short (5 minute) test of working memory.

5. Computerized tests of reaction time and go-no-go to assess the constructs of reaction time and attention.

6. Texas Functional Living Scale is an assessment of practical reading, math, language comprehension and memory developed for individuals with cognitive limitations.

7. ABAS: Adaptive Behavior Assessment Scale to be completed by parent. Queries on functional skills.

8. Wechsler Preschool and Primary Scale of Intelligence-IV (WPPSI-IV), for patients between the ages of 2.5 and 7, is an individually-administered, standardized test that provides scores for verbal and nonverbal domains of intellectual ability. The test requires between 45 minutes and 75 minutes to administer, depending on the age.

9. Wechsler Intelligence Scale for Children-V (WISC-V), for patients 6 years of age through age 17, is an individually administered, standardized test of cognitive ability. This test provides scores for verbal and nonverbal domains of intellectual ability. The test requires between 60 minutes and 90 minutes to administer, depending on age

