## **10. DATA ANALYSIS**

### **10.1 Power calculation:**

We performed a power analysis, in Systat 11. Using a paired Student's t design, comparing measurements on placebo and SGS-742, 16 patients would be needed to detect a change in the Auditory Comprehension subtest of the Neuropsychological Assessment Battery Language Module score of 0.75 SD.

Thus, we are requesting 22 subjects to allow for dropouts. Dropouts will be replaced with new subjects until we attain 16 completers.

We will record the reasons for any dropouts, allowing performance of sensitivity analyses to account for a number of scenarios, including assuming dropouts all had a negative outcome in our analysis of efficacy, and using imputation to model the effects of dropouts based on the profile of each dropout.

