### **10.4 Neuropsychological tests**

The neuropsychological tests were selected by the investigators as representing those assessments which could be completed by this group of patients with adjustments made for the cohort's age group, including WNV (Wechsler Nonverbal Scale of Ability) for patients up to age 22; WAIS-IV (Wechsler Adult Intelligence Scale) for patients age 22 and older; the Neuropsychological

Assessment Battery: Language Module; Rule Shift from the Behavioral Assessment of Dysexecutive Syndrome; Computerized tests of reaction time and go-no-go to assess the constructs of reaction time and attention; Texas Functional Living Scale; ABAS: Adaptive Behavior Assessment Scale to be completed by parent and Queries on functional skills.

The combination of clinical interview, observations, intellectual testing, and executive function tests was devised for a logistically achievable assessment of cognitive and executive function. The testing will be administered at baseline and then at the end of the two six-month treatment arms, which includes a two-month washout period between arms.

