### **11.2. Justification for inclusion of children**

SSADH is a severe pediatric neurotransmitter disease without any effective therapy. The majority of the patients identified are under 18. Patients over the age of four are included because the parent questionnaires measuring activities of daily living as primary outcome data are valid at any age. Early intervention is desirable in a genetic disease.

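### The primary outcome is a single subtest in one place and two measures in others, no rule says what counts as success, and 16 completers are sized on the subtest alone

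*Combined protocol and SAP*

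**What the plan says.** The précis contains both versions. Its Design paragraph states: "The primary outcome measure will be a change in the Auditory Comprehension subtest of the Neuropsychological Assessment Battery Language Module score". Its Outcome Measures paragraph states: "The primary outcome measures for drug efficacy will be performance on neuropsychological testing and responses to parent questionnaire". Section 9.1, which should settle the matter, repeats the second version ("Performance on neuropsychological testing and responses to parent questionnaire") and names no test score and no questionnaire.

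Elsewhere:

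- H1 in section 2.1 predicts improvement on Auditory Comprehension together with "improvements in activities of daily living based on parent questionnaire".
- Section 10.1 uses a paired t design and says that "16 patients would be needed to detect a change in the Auditory Comprehension subtest" of 0.75 SD. It sizes nothing on the questionnaire, and it states no alpha, sidedness or power.
- Section 11.2 justifies enrolment from age 4 on the ground that "the parent questionnaires measuring activities of daily living as primary outcome data are valid at any age".
- Section 4.4.4 lists "ABAS: Adaptive Behavior Assessment Scale to be completed by parent", the only instrument there described as parent-completed. Section 10.4 words the entry as "ABAS: Adaptive Behavior Assessment Scale to be completed by parent and Queries on functional skills". Neither gives the score or domain to be analysed.

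Section 10 contains no success rule, testing order or multiplicity adjustment.

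**The concern.** Suppose the parent questionnaire is significant and Auditory Comprehension is not. Under the précis Design paragraph the trial has failed. Under 9.1, read as allowing either measure to win, it has succeeded. Both readings can be defended from the text, so the choice could be made after the data are seen.

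The missing rule matters in both directions. If either measure may win at the full level, the false-positive rate exceeds the nominal one. If both must win, 16 completers give less power than the single-subtest calculation in 10.1.

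There is also an effect on conduct. Section 17 excuses infrequent missed assessments unless they concern safety or the primary outcome. Whether a missing parent form is excused therefore depends on which version holds.

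**Working it through.** **Inputs from the documents.** Paired t-test; effect 0.75 SD on Auditory Comprehension; 16 completers; 22 enrolled (10.1).

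**Assumptions.**
- Two-sided alpha 0.05, with power 0.80 as the target.
- The 0.75 SD is in units of the SD of the paired difference; 10.1 does not say which SD it means.
- The questionnaire effect is not given. It is taken as 0.75 SD, with 0.50 SD as the alternative.
- The correlation between the two paired differences runs from 0 to 0.7.

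**Step 1: the plan's figure.** Noncentral t with df = n − 1 and noncentrality 0.75 × √n. At n = 16, df = 15 and noncentrality is 0.75 × 4 = 3, giving power 0.801. At n = 15 power is 0.771. So 16 is the smallest n reaching 0.80 for one measure at the full alpha, with nothing reserved for a second.

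**Step 2: either wins, no correction.** With no effect on either measure and correlation 0, the chance that at least one is significant in either direction is 1 − 0.95² = 0.0975. Simulation of two correlated paired t-tests (400,000 runs, n = 16) gives 0.098, 0.095, 0.091 and 0.085 at correlation 0, 0.3, 0.5 and 0.7.

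**Step 3: both required at 0.05 each.** At correlation 0, power is 0.801² = 0.641. Simulation gives 0.664, 0.683 and 0.711 at 0.3, 0.5 and 0.7. With a questionnaire effect of 0.50 SD, power is 0.372, 0.403, 0.424 and 0.447 across the four correlations.

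**Step 4: opposite verdicts.** The Design paragraph and an either-wins 9.1 disagree when only the questionnaire is significant. That probability is the questionnaire's own power minus the power for both.

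| Questionnaire effect | Correlation 0 | Correlation 0.7 |
|---|---|---|
| 0.75 SD | 0.801 − 0.641 = 0.16 | 0.801 − 0.711 = 0.09 |
| 0.50 SD (own power 0.465) | 0.465 − 0.372 = 0.09 | 0.465 − 0.447 = 0.02 |

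If 9.1 instead means that both are required, the disagreement arises when only the subtest is significant. With equal effects this is again 0.16 down to 0.09.

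**Step 5: either wins at 0.025 each.** Power on Auditory Comprehension itself is 0.693 at n = 16. Power for at least one measure is 0.906, 0.872, 0.844 and 0.811 across the four correlations if both effects are 0.75 SD. It is 0.798, 0.763, 0.741 and 0.717 if the questionnaire effect is 0.50 SD.

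**Step 6: completers for 0.80 with both required (0.75 SD each).** 21 at correlation 0, 20 at 0.3 and 0.5, 19 at 0.7. At the plan's 16-of-22 allowance, 19 × 22/16 = 26.1 and 21 × 22/16 = 28.9, so 27 to 29 enrolled.

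**The case against.** The best defence is that the versions are close. Auditory Comprehension is one of the neuropsychological tests, and H1 reads naturally as 9.1 with the test named. That stands, and it narrows the problem to the questionnaire's status and the missing decision rule. It does not remove the problem: H1 still has two components where the Design paragraph has one, and it does not say whether one or both must improve.

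A second defence is that this is a 22-patient phase II trial in a rare disease, with no interim analysis and no stated confirmatory claim. That bears on how elaborate the rule need be. It does not excuse a plan that supports two verdicts on the same data.

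Four stronger readings are tempting but unsupported:

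- A reader might infer that 9.1 makes every test in the 4.4.4 battery primary, especially as section 12 anticipates gains in attention, reaction time and working memory. No test score other than Auditory Comprehension is called primary or used for sizing.
- A reader might count every trial with exactly one significant measure, 32% down to 18%, as a conflict between the Design paragraph and 9.1. That is the disagreement between the either and both readings of 9.1; the conflict with the Design paragraph is half as large.
- A reader might doubt which parent instrument is meant. In 4.4.4 the functional-skills phrase describes ABAS, and 10.4 appears to run the two together. Only the score is missing.
- A reader might conclude that 16 is miscalculated. It is right for a single primary under the assumptions above.

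**Conclusion.** The plan is wrong as written on this point, beyond a lack of detail: the précis contradicts itself, 9.1 and 11.2 follow one version, and 10.1 follows the other.

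With 0.75 SD assumed on both measures, opposite verdicts from the Design paragraph and an either-wins 9.1 arise in about one trial in six at correlation 0 and one in eleven at 0.7. They are rarer if the questionnaire effect is smaller. The excess false-positive rate in step 2 does not depend on any assumed effect.

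The assumed alpha and power reproduce 16 but cannot be confirmed; one-sided 0.05 with 90% power gives 17, which is close. The questionnaire effect and the correlation are wholly assumed. The textual conflict depends on none of these. It needs to be resolved before unblinding, and the documents do not show which rule the sponsor intended.

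**What to change.** Before unblinding, make the précis, H1, 9.1, 10.1 and 11.2 state one rule, with alpha, sidedness and power given and the ABAS score named.

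**Option (a), the cheapest and consistent with 10.1.** Auditory Comprehension, end of SGS-742 versus end of placebo, is the sole primary at two-sided 0.05. The ABAS parent questionnaire is tested next, only if the primary is significant. Sixteen completers stand. The cost is that the questionnaire loses the primary standing it has in 9.1, and 11.2 needs another rationale for enrolling from age 4.

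**Option (b), both stay primary.** Change the précis Design paragraph and state one of two rules:

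- *Either wins, at 0.025 each.* Auditory Comprehension itself then has power of only 0.69. Power for at least one measure is 0.91 down to 0.81 if both effects are 0.75 SD. At 0.50 SD on the questionnaire it is 0.80 down to 0.72, so 16 completers cannot be said to suffice unconditionally.
- *Both required, at 0.05 each.* Restate power at 16 completers as about 0.64 to 0.71. Restoring 0.80 would take 19 to 21 completers, which is hard in so rare a disease.

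Under either option, call the other battery scores exploratory for efficacy only. Neuropsychological tests are safety outcomes under 9.3 and part of the committee's safety review under 15.1, and they should keep that role. The change is to text, with no new data collection unless the sponsor chooses to restore power under the both-required rule.

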### **9.2 Secondary outcome measures for efficacy will be:**

TMS parameters of cortical excitation and inhibition

### **9.3 Outcome measures for safety will include:**

Clinical examination  
Neuropsychological tests

## **10. DATA ANALYSIS**

### **10.1 Power calculation:**

We performed a power analysis, in Systat 11. Using a paired Student's t design, comparing measurements on placebo and SGS-742, 16 patients would be needed to detect a change in the Auditory Comprehension subtest of the Neuropsychological Assessment Battery Language Module score of 0.75 SD.

Thus, we are requesting 22 subjects to allow for dropouts. Dropouts will be replaced with new subjects until we attain 16 completers.

We will record the reasons for any dropouts, allowing performance of sensitivity analyses to account for a number of scenarios, including assuming dropouts all had a negative outcome in our analysis of efficacy, and using imputation to model the effects of dropouts based on the profile of each dropout.

### **10.2 TMS**

Indices for cortical excitability will be obtained including motor threshold (MT), recruitment curve, intracortical inhibition (ICI), intracortical facilitation (ICF), and cortical silent period (CSP) from motor cortex. Motor evoked potential (MEP) size will be measured peak-to-peak in single trials and averages will be calculated for each intensity. ICI and ICF will be studied using a paired stimulus paradigm. CSP onset and termination will be measured in the rectified single trials as the times of the end of the preceding MEP and the return of sustained activity in the EMG, respectively. The conditional averages will be calculated from the single-trial data. These parameters will be compared for intra-individual and inter-individual differences pre- and post-therapy with SGS 742.

### **10.3 MRS**

MRS will be analyzed with the GABA editing sequence provided by the NIH/NIMH MRS Core.

### **10.4 Neuropsychological tests**

The neuropsychological tests were selected by the investigators as representing those assessments which could be completed by this group of patients with adjustments made for the cohort's age group, including WNV (Wechsler Nonverbal Scale of Ability) for patients up to age 22; WAIS-IV (Wechsler Adult Intelligence Scale) for patients age 22 and older; the Neuropsychological

Assessment Battery: Language Module; Rule Shift from the Behavioral Assessment of Dysexecutive Syndrome; Computerized tests of reaction time and go-no-go to assess the constructs of reaction time and attention; Texas Functional Living Scale; ABAS: Adaptive Behavior Assessment Scale to be completed by parent and Queries on functional skills.

The combination of clinical interview, observations, intellectual testing, and executive function tests was devised for a logistically achievable assessment of cognitive and executive function. The testing will be administered at baseline and then at the end of the two six-month treatment arms, which includes a two-month washout period between arms.

### **10.5 CSF analysis**

Quantitation of GABA, GHB, succinic semialdehyde, homocarnosine, 4,5-dihydroxyhexanoic acid (DHHA) and D-2-hydroxyglutaric acid in CSF samples will be achieved using isotope dilution liquid chromatography-tandem mass spectrometry. These metabolites (all of which are interrelated to GABA metabolism) are increased to varying degrees in both CSF derived from SSADH deficient patients and brain tissue derived from SSADH-deficient mice.

In addition, for all CSF samples comprehensive amino acid analysis will be performed. The rationale of this analysis is based upon the clear depletion of glutamine observed in the brain of SSADH-deficient mice. Amino acid analysis is performed by HPLC with ninhydrin post column detection. As well, we have documented in earlier studies that glutamine is low, to borderline-low, in CSF samples derived from SSADH-deficient individuals.

## **11. HUMAN SUBJECTS PROTECTION**

### **11.1 Subject Selection**

Subjects will be selected equitability, based upon their meeting the study's eligibility criteria. Although there is no known human subpopulation incidence variation, the majority of the patients identified have been of 'Caucasian' background.

### **11.2. Justification for inclusion of children**

SSADH is a severe pediatric neurotransmitter disease without any effective therapy. The majority of the patients identified are under 18. Patients over the age of four are included because the parent questionnaires measuring activities of daily living as primary outcome data are valid at any age. Early intervention is desirable in a genetic disease.

### **11.3 Justification for inclusion of vulnerable subjects**

Patients with SSADH deficiency frequently have cognitive impairment and may lack consent capacity. The effect of SGS-742 on neuropsychological function is one of the main outcome measures of the protocol.

### **11.4 Justification of sensitive procedures (using placebo)**

Placebo-controlled studies are the best way to obtain reliable data on drug efficacy in a clinical trial in any neurological disorder. Patients will still be on their baseline drug therapy during all treatment phases, and will not be exposed to any risk greater than their standard therapy while on placebo.

### **11.5 Safeguards for vulnerable populations**

Protections for vulnerable populations will include evaluation by the HSPU/ACAT, obtaining consent from DPA for adults without capacity, assent from participants, pregnancy testing for women of childbearing potential, and use of pediatric-trained staff and facilities. Dissent will be respected.

## **12. ANTICIPATED BENEFIT**

The clinical trial has the prospect of direct benefit to the patients with SSADH deficiency since the patients may show improvement on neuropsychological testing in the areas of attention, reaction time, visual information, and working memory during treatment with SGS-742.

The clinical trial is likely to result in generalized knowledge about the effect of GABAB antagonists on cerebral function, thereby possibly leading to new diagnostic and/or treatment options for individuals with other disorders as well as SSADH deficiency, especially neurometabolic disorders featuring epilepsy.

## **13. CLASSIFICATION OF RISK (FOR THE STUDY AS A WHOLE)**

For adults the study is more than minimal risk due to the paired pulse TMS.

For Adults without consent capacity the study is research involving a minor increment over minimal risk due to the paired pulse TMS presenting the prospect of direct benefit to the individual

For Children the study is 45CFR46.405 Research involving greater than minimal risk but not more than a minor increment over minimal risk, due to the paired pulse TMS but presenting the prospect of direct benefit to the individual child

Overall risk and benefit consideration

The risks are reasonable in relation to anticipated benefit

## **14. CONSENT DOCUMENTS AND PROCESS**

Study investigators designated as able to obtain consent in section 11.6 above, will obtain informed consent. Each subject will receive an oral and written explanation of the purposes, procedures, and risks of this study in a language appropriate for the individual's level of understanding. A copy of the signed consent form will be placed in the medical record, and a copy will be given to each study participant. A member of the protocol team will be available to answer questions about the study to be performed. Assent will be obtained from minor subjects age 8 and older, when possible, and adults found not capable of giving informed consent.

If a non-English speaking participant is unexpectedly eligible for enrollment, the CC standard short written consent form in the appropriate language and a written summary of what the Investigator will say to the participant will be used as part of an oral consent process. The IRB approved English written consent form will serve as the written summary if the short form process is used. The investigator will obtain an interpreter unless the investigator is fluent in the prospective participant's language. Preferably, the interpreter will be someone who is independent of the participant (i.e., not a family member). Interpreters will be found through the Department of Social Work. The interpreters will translate the current IRB-approved English version of the consent verbatim and facilitate discussion between the participant and investigator.

The written summary will be signed by the investigator obtaining consent and a witness to the oral presentation. The short written consent form will be signed by the participant and a witness who observed the presentation of information. The interpreter may sign the consent document as the witness and, in this case, will note "Interpreter" under the signature line. A copy of the signed form will be provided to the participant to take home.

The investigator obtaining consent will document the consent process in the participant's medical record, including the name of the interpreter. Further, all instances of use of the short form process will be reported to the IRB at the time of annual review.

The consent form contains all required elements

The consent documents submitted with this protocol include adult patient or parent consent, as well as adult and minor assent forms.

